5.3 On-Study Evaluations

(See study calendar, section 5.10)

1. Physical exam: including complete skin evaluation and evaluation of oral mucosa prior to start of **each** RT cycle and **prior** to each LY2157299 administration.
2. Hematology: CBC with differential and platelet count and peripheral blood smear. PT/INR,PTT should be evaluated following multiple doses of LY2157299; Serum chemistries: Electrolytes (sodium, potassium, chloride, and bicarbonate), BUN, creatinine, glucose, and liver function tests (AST, ALT, ALP, total bilirubin, LDH, and Troponin I C). These will be carried out prior to start of each RT cycle and prior to each cycle of 2 weeks of BID LY2157299 administration.
3. ECHO/Doppler : Week 8 within 5 days prior to starting week 9 LY2157299 administration and Week 15
4. Study Special Tests: TGF β levels (at wk 1 day -1 and week 15 visit), immune evaluation at weeks 1 day -1, 2, 5 and 15 LY2157299 PK (pre- & after completion of drug cycle day 14 & at day 42).
5. Tumor measurement by PET/CT/ CT(chest/abdomen/pelvis) at weeks 5 and 15.
6. Adverse events evaluated and recorded using the NCI CTCAE version 4.0 throughout the treatment period (weeks 0-15).

To date, LY2157299 at the planned dose for this study is well tolerated in patients. If a toxicity is observed, a dose reduction may be considered based on the aggregate safety information of LY2157299, if other plausible reasons for a toxicity have been excluded.

Specifically, no bone marrow toxicities were detected in nonclinical toxicology studies; 1 toxicity was reported in a patient with glioblastoma in whom a Grade 4 thrombocytopenia was observed and this toxicity was potentially associated with administration of LY2157299 monotherapy. If a similar case occurs, the drug should be discontinued until platelet counts either return to Grade 1 or baseline.

If a patient experiences any of the following events that are considered possibly related to LY2157299 and not to study disease, LY2157299 will be omitted until the event resolves:

- Grade 4 Thrombocytopenia
- Grade 3 thrombocytopenia associated with bleeding
- Grade 4 Anemia
- absolute neutrophil count (ANC) $<0.5 \times 10^9/L$ for longer than 7 days, or ANC $<1.0 \times 10^9/L$ with a single temperature of $>101^{\circ}\text{F}/38.3^{\circ}\text{C}$ or a sustained temperature of $>100.4^{\circ}\text{F}/38^{\circ}\text{C}$ for more than 1 hour, or platelet count $<25,000 \times 10^9/L$

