- Common Terminology Criteria for Adverse Events Grade 3 or 4 non-hematologic toxicity

Non-hematologic and hematologic toxicity must resolve to CTCAE Grade 0, 1, or baseline (with the exception of alopecia, fatigue, skin rash, nausea, vomiting, constipation, or diarrhea that can be controlled with treatment) before start of next cycle. If recovery is >29 days (Day 1 of the next cycle), patient must be withdrawn from study treatment.

If moderate or severe heart valve toxicities are observed, or the patient develops aneurysms of the great vessels of the heart, the patient must immediately be discontinued from the treatment and the toxicity reported to sponsor within 24 hours (see references on the ECHO assessment based on the Guidelines of the American and European Societies of Cardiac Echocardiography). If the patient develops new cardiovascular lesions in the chest, an MRI or CT with contrast of the abdomen should be performed to evaluate for development of abdominal vascular lesions. Exceptions to this rule must be approved by the IRBs and sponsor.

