11.1 Anti-tumor Effect

11.1.1 Definitions

Patients will be evaluated by PET/CT or CT(chest/abdomen/pelvis) at baseline, week 5 and week 15. However, systemic anti-tumor response will be by PET/CT or CT(chest/abdomen/pelvis) as defined by irRC at 15 weeks (primary endpoint).

Patients who have received at least one 14 days cycle of the study drug will be followed for toxicity (lack of grade 4 toxicity— primary safety end point). Patients will receive a total of 14 doses of LY2157299 (one dose daily for 14 consecutive days), per cycle. Patients who have received any treatment will also be evaluated for abscopal response to the metastatic sites using the immunologic response criteria based on the 5 and 15 week PET/CT or CT(chest/abdomen/pelvis) scans as outlined above in Table 2.

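### The only primary safety measure, lack of grade 4 toxicity after at least one cycle, counts as safe some patients whose drug was stopped or omitted for toxicity, and Section 13 plans no toxicity estimate

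*Combined protocol and SAP*

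**What the plan says.** The Protocol Summary, Section 1.1 and Section 14.1.1 all list safety and feasibility of the combination as the first primary objective or endpoint. None of them attaches a measure. The measure appears once, in Section 11.1.1: "lack of grade 4 toxicity— primary safety end point". The same sentence fixes the set: "Patients who have received at least one 14 days cycle of the study drug will be followed for toxicity".

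Section 5.3 sets out when the drug is held or stopped. For listed events that are "considered possibly related to LY2157299 and not to study disease, LY2157299 will be omitted until the event resolves", the list includes:

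- "Grade 3 thrombocytopenia associated with bleeding";
- an absolute neutrophil count (ANC) below 1.0 x 10^9/L "with a single temperature of" above 38.3°C, or with a sustained fever;
- "Common Terminology Criteria for Adverse Events Grade 3 or 4 non-hematologic toxicity".

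A separate paragraph requires immediate discontinuation "If moderate or severe heart valve toxicities are observed, or the patient develops aneurysms of the great vessels of the heart", and states no CTCAE grade. Section 5.3 also withdraws a patient from treatment when recovery from toxicity takes more than 29 days.

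Section 13 plans exact 95% limits for clinical and immune response rates, mixed models for the immune parameters, and accuracy measures for the gene signature. It names no toxicity rate. The analysis-population paragraph under 14.1.2 defines efficacy sets only.

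**The concern.** The protocol judges certain events serious enough to interrupt or end treatment, but its primary safety measure does not register them unless they reach grade 4. This matters most for valve and aneurysm events. Section 2.2.3 reports vascular degeneration at the base of the aorta in dogs and rats, with aneurysms and deaths in rats, and requires cardiac monitoring because of the animal cardiac findings. A patient taken off LY2157299 for an aneurysm graded below 4 would still be a success on the stated measure.

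The set adds a second gap. If follow-up for the endpoint requires one full 14-day cycle, a patient who stops on day 8 for toxicity may be outside the denominator, even if that toxicity was grade 4.

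At stake is the reported result for the first primary objective. The drug actions are pre-specified, but the way these events enter the safety result is not, so that choice could be made after the data are seen.

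**Working it through.** **1. The plan's own figures.** The plan states no safety figure to reproduce: no threshold, expected rate or precision. Its one decision rule concerns response, and it reproduces. With X ~ Binomial(28, p) and success at X ≥ 4, P(X ≥ 4 | p = 0.05) = 0.0491 and P(X ≥ 4 | p = 0.19) = 0.8065, against the stated alpha of 0.05 and power of 80%. Toxicity does not enter this rule.

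**2. Section 5.3 set against Section 11.1.1.**

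| Section 5.3 rule | Action | Grade 4 required by the rule? | Always counted by 11.1.1? |
|---|---|---|---|
| Grade 4 thrombocytopenia or Grade 4 anemia, possibly related | Omit | Yes | Yes |
| Grade 3 thrombocytopenia with bleeding, possibly related | Omit | No | No |
| ANC < 1.0 x 10^9/L with fever, possibly related | Omit | No | Only if graded 4 |
| Grade 3 or 4 non-hematologic toxicity, possibly related | Omit | No | Only if graded 4 |
| Moderate or severe valve toxicity, or great-vessel aneurysm | Discontinue | No grade stated | Only if graded 4 |
| Recovery longer than 29 days | Withdraw | No | Only if the event was graded 4 |

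The last column assumes that the patient is in the 11.1.1 set. The mismatch is partial: some rules match the endpoint and five do not.

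**3. The set.** Suppose 28 patients are treated and one stops for a grade 4 event before completing a cycle. On the plain reading of 11.1.1 the result is 27/27 = 100%. In all treated patients it is 27/28 = 96.4%. Section 8.2 follows adverse events after any administration of the drug, so the data on that patient would exist.

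**4. What one uncounted patient does to the figure.** Each treatment-limited patient not counted by the measure changes the event-free proportion by 1/n. The documents give three candidate sizes: 28 planned, 35 as the accrual ceiling in the Protocol Summary, and up to 56 in the sample size paragraph. So 1/28 = 3.6, 1/35 = 2.9 and 1/56 = 1.8 percentage points.

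**5. Illustration with assumed counts.** The counts 1 and 5 are chosen, not taken from the documents. Assume no grade 4 event and x patients with a Section 5.3 event below grade 4. With s = n − x, the exact limits are the 2.5% point of Beta(s, x + 1) and the 97.5% point of Beta(s + 1, x). For x = 0 the lower limit is 0.025^(1/n), which for n = 28 is 87.7%.

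| n | Measure as written (any x) | Counting 5.3 events, x = 1 | Counting 5.3 events, x = 5 |
|---|---|---|---|
| 28 | 100% (87.7 to 100) | 96.4% (81.7 to 99.9) | 82.1% (63.1 to 93.9) |
| 35 | 100% (90.0 to 100) | 97.1% (85.1 to 99.9) | 85.7% (69.7 to 95.2) |
| 56 | 100% (93.6 to 100) | 98.2% (90.4 to 100.0) | 91.1% (80.4 to 97.0) |

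The first column of results does not move, whatever happens below grade 4. Across the chosen counts the difference runs from 1/56 = 1.8 to 5/28 = 17.9 points. This shows how the measure behaves; it does not predict the trial's result.

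**The case against.** The strongest reply is that a dosing rule is not an endpoint. Section 5.3 sets cautious thresholds, most of its events only suspend the drug until they resolve, and nothing obliges the endpoint to mirror them. The grade 4 phrase is a parenthesis in a section on anti-tumor effect, and nothing forbids reporting lower grades. Lower grades are also handled elsewhere. All adverse events are graded, attributed and held in REDCap, and five or more Grade 3 or higher non-hematological toxicities in 3 months pause the combination (12.2). The DSMB performs an annual safety analysis (12.1).

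Much of this stands. Patient protection does not depend on the 11.1.1 phrase, and the documents do not contradict themselves. It is also true that they do not show what grade a valve or aneurysm event would receive, and that the separate ECHO protocol is not available here.

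It does not answer the narrower point. The phrase is labelled the primary safety endpoint and is the only measure given. The 12.2 pause counts toxicities rather than patients, leaves out hematologic events and yields no estimate. Collecting data and overseeing them do not say how a patient taken off drug below grade 4 enters the primary result.

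A reader might infer more: that patients are unprotected, that lower-grade events go unrecorded, or that an unsafe combination could be carried forward because of this wording. The documents support none of these. The capture, pause and review provisions above deal with the first two. On the third, the go/no-go rule uses responses alone, so it would be the same under any safety measure.

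**Conclusion.** The point holds as a gap in how the primary safety result is defined and analysed. Five Section 5.3 rules can hold, stop or end treatment without grade 4 being reached, and the only stated measure does not count such patients. The 11.1.1 set can also exclude patients who stop for toxicity in the first cycle. Section 13 plans no toxicity estimate that would fill the gap.

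Its size cannot be estimated, because the documents give no human rate for these events, no acceptable limit and no fixed safety denominator. All that follows is the arithmetic of 1.8 to 3.6 points per affected patient. The conclusion rests on reading 11.1.1 literally, both the grade and the completed cycle. Read just as literally, the phrase does not name grade 5, which a small wording change resolves.

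No stated figure, threshold or decision changes. This is a cheap improvement to the reporting of the first primary objective.

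**What to change.** In Section 11.1.1, keep the grade 4 proportion and word it as grade 4 or higher. In 11.1.1 and Section 13, add a second primary safety summary: the proportion of patients with any event meeting a Section 5.3 omission, discontinuation or withdrawal rule. Name the components:

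- the hematologic rules, including Grade 3 thrombocytopenia with bleeding and ANC below 1.0 x 10^9/L with fever;
- possibly related Grade 3 or 4 non-hematologic toxicity;
- moderate or severe valve toxicity or great-vessel aneurysm, whatever the grade;
- recovery taking more than 29 days.

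Report each component and the composite with exact 95% limits. Use all patients who received any LY2157299 as the main set, and the at-least-one-cycle set as supportive. Shift tables for troponin I and echo findings are optional; the echo table depends on what the ECHO protocol has sites record.

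The cost is wording in two sections and a few tables. No new assessments or patients are needed, because adverse events with grade and attribution are already collected. The reported safety figure may look less favourable.

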Short Title:	LY2157299 and Radiotherapy in Metastatic Breast Cancer
Clinical Phase:	Phase II
Principal Investigator:	[name], M.D.
Sample Size:	N= 28 (WCM will enroll a total of 18 patients and UCLA will enroll 10 patients)
Accrual Ceiling:	35
Study Population:	Patients must have biopsy proven metastatic breast cancer and have stable disease or progressed after at least one course of chemotherapy or hormonal therapy. This study will not enroll vulnerable population. Women > 18 years and < 90 years.
Accrual Period:	3 years
Study Design:	TGFB blockade will enhance response of irradiated tumors and improve the function of Dendritic and T cells. Patients will receive 300 mg/day of study drug administered via oral drug tablet every day for 14 days on and 14 days off (=28 day cycle). Radiation to a metastatic site will be delivered at a dose of 7.5 Gy, given consecutively on days 1-3-5.
Study Duration:	Study participation will involve 15 visits over the course of 16 weeks (approx.4 months). Patients will have an annual follow-up up to 5 years.
Study Agent/	
Intervention Description:	LY2157299 will be administered oral drug tablet: 300mg/day. Patients will receive 300 mg/day of study drug administered via oral drug tablet every day for 14 days on and 14 days off (=28 day cycle) .
Primary Objective:	1. to assess safety and feasibility of combining TGFβ receptor I kinase inhibitor LY2157299 and local radiotherapy 2. To determine if treatment with TGFB receptor I kinase inhibitor LY2157299 and localized RT achieves an abscopal tumor regression;
Secondary Objectives:	1. to estimate the local response rate of combining TGFB receptor I kinase inhibitor LY2157299 and local radiotherapy 2. To determine if treatment with TGFB receptor I kinase inhibitor LY2157299 and localized RT enhances tumor-specific immunity in

patients with metastatic breast cancer, and if this is associated with abscopal tumor regression.

3. To determine if treatment with TGFB receptor I kinase inhibitor LY2157299 and localized RT alters the numbers and function of T-reg cells in patients with metastatic breast cancer.

Endpoints:

Primary Endpoint: A. To assess safety and feasibility of combining TGF β receptor I kinase inhibitor LY2157299 and local radiotherapy
B. To determine if treatment with TGFB receptor I kinase inhibitor LY2157299 and localized RT achieves an abscopal tumor regression

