5. TREATMENT PLAN

5.1 Investigational Agent or Device Administration

Enrolled patients will receive 300 mg/day of LY2157299. LY2157299 will be administered as an oral drug tablet.

The study drug will be administered orally on a 28-day cycle (1 cycle=28 days), every 2 weeks, or 14 days on / 14 days off. Blood samples will be obtained at baseline, and weeks 2, 6 and 15 for immune monitoring. Imaging by PET/CT or CT(Chest/Abdomen/Pelvis) will be performed at baseline, 5 weeks and 15 weeks. The chosen metastatic sites will receive conformal external beam radiation 7.5 Gy/fraction x 3, to a total of 22.5 Gy over the course of one week (on alternating days):

- lesion 1 will be irradiated at week 1 (RT starts 1 day after 1st dose of LY2157299),
- lesion 2 will be irradiated at week 5 (RT starts after 1stdose of the second cycle of LY2157299)

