7 DOSING DELAYS/DOSE MODIFICATIONS

LY2157299 will be administered as a flat dose of 300 mg/day, divided in a BID administration of 150 mg each, as an oral tablet.

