14.1.2 Secondary endpoints

1. To estimate the local response rate of combining TGF β receptor I kinase inhibitor LY2157299 and local radiotherapy
2. To determine if treatment with TGF β receptor I kinase inhibitor LY2157299 and

localized RT enhances tumor-specific immunity in patients with metastatic breast cancer, and if this is associated with abscopal tumor regression.

3. To determine if treatment with TGF β receptor I kinase inhibitor LY2157299 and localized RT alters the numbers and function of T-reg cells in patients with metastatic breast cancer.

A. Analysis Populations

Efficacy analysis will be conducted on all patients who are entered into the study and received any treatment. Additional supportive efficacy analyses will be conducted for those patients who have completed week 15 visit.

B. Sample Size

i. Accrual estimates

Expected number of eligible patients will be 4 per month.

ii. Sample size justification

In this trial, a total of 28 patients with metastatic breast cancer will be accrued both at WCM and at UCLA (18 patients at WCM and 10 patients at UCLA) to treatment with radiotherapy + 300 mg/daily LY2157299 for 14 days on / 14 days off, and followed for evaluation of abscopal responses based on the immune response criteria at 15 weeks. With 28 patients enrolled in this study, we can test the null hypothesis that the abscopal response rate at 15 weeks is ≤ 0.05 versus the alternative that the response rate is 0.19 with $\alpha = 0.05$ and power of 80%. If there are 3 or fewer responses in the 28 patients, then the combination will be rejected for further study in this single stage design (calculations from PASS 2008, J. Hintze, NCSS, Kaysville, Ut). The trial is designed to allow for up to 56 patients to be enrolled to ensure that 28 patients will be evaluable at 15 weeks. Response rates will also be estimated for all enrolled patients.

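### Section 11.1.1 gives one dose daily (14 per cycle) where Sections 7 and 5.3 give twice-daily dosing (28 per cycle): an internal inconsistency in frequency, dose size and dose count

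*Combined protocol and SAP*

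**What the plan says.** Three sections of the combined protocol and SAP say how the daily amount is taken.

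- Section 11.1.1 (Definitions): "Patients will receive a total of 14 doses of LY2157299 (one dose daily for 14 consecutive days), per cycle". It directly follows the sentence that sets who is followed for the primary safety endpoint.
- Section 7, in its only sentence: "LY2157299 will be administered as a flat dose of 300 mg/day, divided in a BID administration of 150 mg each, as an oral tablet".
- Section 5.3 (On-Study Evaluations), on the timing of laboratory tests: "prior to each cycle of 2 weeks of BID LY2157299 administration".

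Three other places give the daily total and the on/off pattern but no frequency within the day.

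- Protocol Summary: "300 mg/day of study drug administered via oral drug tablet every day for 14 days on and 14 days off".
- Section 5.1, the administration section: "Enrolled patients will receive 300 mg/day of LY2157299", given "every 2 weeks, or 14 days on / 14 days off".
- Section 14.1.2, sample size justification: "radiotherapy + 300 mg/daily LY2157299 for 14 days on / 14 days off".

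All of this is current text, and none of it comes from the summaries of changes. No visible section ranks one statement above another or defines a dose as the whole day's amount.

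**The concern.** A count of 14 doses, explained as one per day, cannot be squared with a twice-daily split over the same 14 days. Section 5.1, where a reader would look first, does not settle it because it is silent on frequency.

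The first primary objective is the safety and feasibility of this drug combined with radiotherapy, so a safety result should say which regimen it describes. As written, the report could cite Section 11.1.1 for one regimen or Section 7 for another. Anyone who summarises treatment delivery as doses taken over doses planned would also have two possible denominators, a factor of two apart.

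**Working it through.** **Inputs**

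- Treatment days per cycle: 14 (Protocol Summary, Sections 5.1, 11.1.1 and 14.1.2, study calendar footnote).
- Daily total: 300 mg (Protocol Summary, Sections 5.1, 7 and 14.1.2).
- Administrations per day: 1 (Section 11.1.1) or 2 (Sections 7 and 5.3).
- Size of each administration: 150 mg is printed in Section 7. Section 11.1.1 prints no size; 300 mg follows if the stated daily total is taken as a single dose.

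**Dose count.** Administrations per cycle = treatment days × administrations per day.

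- Section 11.1.1: 14 × 1 = 14. The section's own figure reproduces.
- Sections 7 and 5.3: 14 × 2 = 28. This number is not printed; it follows from the twice-daily wording.

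**Amount per cycle.** Administrations × size.

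| Reading | Administrations | Size | Per day | Per cycle |
|---|---|---|---|---|
| Section 11.1.1 with the stated daily total | 14 | 300 mg | 300 mg | 4,200 mg |
| Section 7 | 28 | 150 mg | 300 mg | 4,200 mg |
| Section 7 size with the Section 11.1.1 count | 14 | 150 mg | 150 mg | 2,100 mg |

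The first two rows agree on the total. The third shows that the two sections cannot be combined: it gives half the daily amount stated everywhere else.

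**Effect on a dose-count measure.** Suppose compliance is doses taken divided by doses planned. The plan specifies no such measure, so this is an illustration.

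- A patient who takes all 28 twice-daily doses, scored against 14: 28/14 = 200%.
- A patient who takes 14 of the 28, scored against 14: 14/14 = 100%. Scored against 28: 14/28 = 50%.

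**Effect on the design.** Section 14.1.2 tests a 15-week abscopal response rate of at most 0.05 against 0.19 in 28 patients, and rejects the combination at 3 or fewer responses, so success needs at least 4. The exact binomial gives:

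- P(X ≥ 4 | n = 28, p = 0.05) = 0.0491, against a stated alpha of 0.05;
- P(X ≥ 4 | n = 28, p = 0.19) = 0.8065, against a stated power of 80%.

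Dosing frequency enters neither calculation.

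**Effect on the populations.** Safety follow-up in Section 11.1.1 requires at least one 14-day cycle, counted in days. The efficacy population in Section 14.1.2 is every entered patient who received any treatment. Neither depends on whether a cycle holds 14 or 28 doses.

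**The case against.** The best defence is that this is loose wording, not two competing regimens. The protocol does use dosing terms loosely. Section 5.3 asks for a physical examination before each administration of the drug, while the study calendar schedules examinations only at intervals, so administration there seems to mean a course of treatment. One dose daily might likewise mean the day's 300 mg. The two sections that do give a twice-daily split agree with each other, and Section 11.1.1 is about measuring effect. Section 2.2.1, on pharmacokinetics, is redacted and may say something on frequency.

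This makes a drafting slip plausible and limits how serious the point is. It does not remove the mismatch: Section 11.1.1 is worded as what patients will receive, gives a count, and explains that count as one per day.

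A reader might infer more than the documents support.

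- *That the treatment under test is undefined.* The daily total, the cycle total and the on/off pattern agree wherever they appear.
- *That regimen will be confounded with site (18 and 10 patients).* Nothing shows the sites reading the protocol differently. Section 13 uses site only to describe patients and their disease, and no between-site comparison of outcomes is planned.
- *That peak exposure and the PK results will differ.* With Section 2.2.1 redacted, the effect of splitting the dose cannot be judged. PK is neither an objective nor an endpoint, and Section 13 gives no PK analysis.
- *That the count of completed cycles will differ.* A cycle is defined in days.

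**Conclusion.** The point stands in its narrow form, as an internal inconsistency and not a questionable design choice. Section 11.1.1 conflicts with Sections 7 and 5.3 by a factor of two in administrations per cycle (14 against 28) and, with the daily total held at 300 mg, by a factor of two in the size of each dose (300 mg against 150 mg). No effect on any endpoint estimate is shown.

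The ambiguity touches three things: the instruction on how the drug is taken, any dose-count summary of exposure or compliance, and the description of the regimen to which the primary safety result applies. It merits correction because safety of the combination is a primary objective and the correction is nearly free.

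This rests on two assumptions: that a dose in Section 11.1.1 means one intake, since no visible text says otherwise, and that the redacted text does not settle the matter.

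**What to change.** Reconcile Sections 11.1.1, 7 and 5.3 so that all three give one within-day frequency and one number of doses per cycle. Add the frequency to Section 5.1, where it is missing. If exposure or compliance will be reported as a dose count, name the denominator in the same terms. Which regimen is intended is for the sponsor and investigator to state; this review takes no position.

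The cost is a wording amendment to Section 5.1 and to whichever of the three sections proves wrong, plus a short memo to both sites. The sample size, decision rule, analysis populations and analyses do not change.
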